***The use of an embolic protection device during the TAVI procedure is not permitted.***

### Pre-Procedure

- Pre-medication recommendations:
  - If the subject is currently on warfarin therapy, or local equivalent, prior to the procedure:
    - Discontinue warfarin therapy 3 days prior to the procedure
    - Confirm that the INR < 1.8 prior to the procedure
    - Administer antiplatelet therapy:
      - Aspirin (75- 325 mg) daily **or**
      - Clopidogrel (75 mg) daily (or ticlopidine if clopidogrel is contraindicated) for 3 days prior to the procedure
  - If the subject is currently **not** on warfarin therapy prior to the procedure:
    - Aspirin (75-325 mg) on the day of the procedure **and**
    - Clopidogrel (300 mg)
  - Consider adjunctive proton pump inhibitors, H2 antagonists or antacids
- Routine Laboratory Tests:
  - Complete Blood Count
    - White Blood Count
    - Hematocrit
    - Hemoglobin
    - Platelet Count
  - Creatinine and Creatinine Clearance
    - If the GFR < 60 cc/min, consider:
      - Fluid hydration on the day prior to the procedure
      - Discontinuation of NSAIDs and ACE inhibitors
  - Cardiac Enzymes (CK/CK-MB)
  - International Normalized Ratio (INR), if applicable
  - Activated Partial Thromboplastin Time (aPTT)
  - B-type Natriuretic Peptide (BNP) or NT-proBNP
  - Liver Panel:
    - ALT
    - AST
    - Albumin
  - Sodium
  - Potassium
- 12-lead Electrocardiogram (ECG)

### TAVI Procedure

- *Medications*

One hour prior to the procedure, prophylactic antibiotic therapy of the Investigator's choice should be initiated:

  - Cefuroxime 750mg intravenous (IV) 1 hour pre-procedure, then 6 hours and 12 hours post-procedure
  - If allergic to Penicillin, prescribe Vancomycin 1g IV
  - Consider holding anti-hypertensives
- *Anesthesia and Procedural Set Up*
  - Establish a central venous line
  - Administer general anesthesia or conscious sedation per hospital protocol
  - Prior to beginning the investigational TAVI device system implant, place a temporary 4-5 Fr. balloon-tip pacing wire in a stable location within the right ventricular (a screw-tip wire may be used for more secure placement for subjects at high-risk for dislodgement, if necessary)
  - Whenever possible, use the upper torso venous system (eg. jugular, subclavian) for temporary pacing wire access
  - Use fluoroscopy to guide wire placement and stability
  - Confirm sensing and capture
  - Program the backup pacing rate to minimize ventricular pacing (eg. 30-40 bpm). If heart block develops, adjust the rate accordingly
  - Record ECG and angiogram during the procedure
- *Vascular Access*

- The primary access artery will be used to introduce the CoreValve device and the balloon catheter; the secondary access artery will be used to introduce the reference pigtail
- Insert a 6Fr introducer sheath into the secondary access artery
- Insert 18Fr introducer sheath into the primary access artery using hospital protocol (either percutaneously or surgical cut down)
- Administer anticoagulant therapy according to hospital protocol. If heparin is administered as an anticoagulant, check activated clotting time (ACT) at five minutes and monitor every 30-60 minutes after initial bolus of heparin
- Maintain ACT  $\geq$  250 seconds
- Anticoagulant may be administered at any time prior to this point, but avoid delaying beyond this point
- *Crossing the native valve*
  - Advance the graduated pigtail catheter to the ascending aorta and position the distal tip in the noncoronary cusp of the native aortic valve
  - Identify the ideal annular viewing plane using contrast injections at various angiographic angles, preferably in the left anterior oblique (LAO) projection.
    - An aortogram with the three aortic cusps aligned in one (1) plane should be obtained in order to proceed with the procedure and guarantee an optimal working view for eventual implantation
  - Insert an angiographic catheter over a standard, J-tip guidewire into the primary access sheath and advance to the ascending aorta
  - Exchange the J-tip guidewire for a 0.035-in (0.889-mm) straight-tip guidewire. Advance the straight-tip guidewire across the native aortic valve into the left ventricle
  - After crossing the native aortic valve with the guidewire, advance the angiographic catheter into the left ventricle
  - Exchange the straight-tip guidewires for an exchange-length J-tip guidewire
  - Exchange the angiographic catheter for a 6Fr pigtail catheter
  - Remove the guidewire and connect the catheter to the transducer. Using both catheters, record the aortic pressure gradient
  - Using a right anterior oblique (RAO) projection, advance previously pigtail-shaped, 0.035-in (0.889-mm) high-support guidewire through the pigtail catheter and position in the apex of the left ventricle
  - Remove the pigtail catheter while maintaining guidewire position in the left ventricle
- *Rapid Pacing and Pre-dilatation of the Implant site*
  - Insert the valvuloplasty balloon through the 18Fr introducer sheath and advance it to the ascending aorta
  - Perform a rapid pacing test. A successful test is defined as 1-to-1 pacing capture with an immediate drop in pressure and elimination of the systolic-diastolic waveform
  - Reposition the angiographic equipment to the ideal viewing plane as previously described. Position the valvuloplasty balloon across the native valve, while maintaining strict fluoroscopic surveillance of the distal tip of the guidewire in the left ventricle (LV)
  - Perform BAV per hospital protocol and remove the valvuloplasty balloon while maintaining guidewire position across the native aortic valve
  - Balloon sizing directed to 1:1 sizing of the minimal annular diameter by computerized tomographic angiography (CTA) or echocardiogram with maximum 25 mm balloon
  - Perform full balloon expansion

- *Medtronic CoreValve™ Implantation*
  - Insert the device over the 0.035-in (0.889-mm) guidewire and advance it, while maintaining strict fluoroscopic surveillance of the guidewire in the LV
  - When crossing the aortic arch, control the guidewire preventing it from moving forward
  - Advance the device through the native valve. Perform an angiogram to confirm that the graduated pigtail catheter is in position within the noncoronary cusp of the aortic root, preferably in the shallow LAO projection
  - Use Fluoroscopy to identify the appropriate landmarks
  - Place the bioprosthesis within the aortic annulus. Optimal placement of the bioprosthesis is 4 mm - 6 mm below the annulus. The annulus is defined as the angiographic floor of the aortic root
  - After attaining optimal catheter position, slowly turn the micro knob and begin to deploy the bioprosthesis. As the inflow aspect of the bioprosthesis starts to flare outward, monitor bioprosthesis position under fluoroscopy
  - Caution: During implantation, if resistance to deployment is encountered (for example, the micro knob starts clicking or is tight or stuck), apply mild upward pressure to the macro slider while turning the micro knob. If the bioprosthesis still does not deploy, remove it from the patient and use another system
  - Perform an angiogram. Once annular contact is made, the bioprosthesis should not be advanced into a lower position
  - Continue deploying rapidly to the 2/3 deployment point; stop turning the micro knob
  - Perform an angiogram to assess the location of the bioprosthesis.
  - If the bioprosthesis is positioned low, carefully pull the DCS to reposition the bioprosthesis
  - Evaluate the valve position and valve function using hemodynamic, aortography, and possible echocardiography
  - When satisfactory position is achieved, continue to turn the micro knob until both frame loops disengage
  - Use orthogonal views under fluoroscopy to confirm that the frame loops have detached from the catheter tabs. If a frame loop is still attached to a catheter tab, under fluoroscopy, advance the catheter slightly and, if necessary, gently rotate the handle clockwise (<math><180^\circ</math>) and counterclockwise (<math><180^\circ</math>) to disengage the loop from the catheter tab
  - Withdraw the DCS carefully to the aorta avoiding contact with the inflow portion of the frame while maintaining guidewire position
- *Medtronic CoreValve™ Post Deployment*
  - Close the DCS capsule and remove the DCS through the 18Fr introducer sheath
  - Advance a 6Fr pigtail catheter over the guidewire into the left ventricle
  - Remove the guidewire and connect the pigtail catheter to the transducer
  - Using both pigtail catheters, record aortic pressure gradient
  - Withdraw 6Fr pigtail
  - Perform post-implant aortogram with the reference pigtail to assure coronary patency and assess aortic regurgitations. Aortogram Acquisition Guidelines are located in **Appendix R.6**
  - Remove the 18Fr introducer sheath and complete the puncture site closure per hospital protocol
  - Perform contrast angiography of the primary vessels to verify the absence of any vascular complications with the reference pigtail
  - Remove the reference pigtail catheter over a standard guidewire
  - Remove the 6Fr introducer and close the access site per hospital protocol

- **Medtronic CoreValve™ Evolut R™ Implantation**
  - Prepare the vascular access site according to standard practice
  - Predilate the native aortic valve with an appropriate diameter valvuloplasty balloon
  - Backload the catheter onto the guidewire. Insert the catheter tip and capsule through the access site, while maintaining the EnVeo InLine™ sheath tip against the proximal end of the capsule. Then, insert the EnVeo InLine™ sheath through the access site, maintaining contact with the capsule. Maintain guidewire position across the aortic valve. Confirm the position of the trigger before crossing the aortic arch
  - Under fluoroscopic guidance, advance the catheter and EnVeo InLine™ sheath over the guidewire to the aortic annulus. Do not rotate the catheter as it is advanced; rotating the handle does not rotate the capsule
  - Position the catheter so that the bioprosthesis is at the optimal depth relative to the valve annulus
  - To deploy the bioprosthesis, rotate the blue actuator in the direction of the arrows. The capsule retracts and exposes the bioprosthesis. Continue deploying the bioprosthesis in a controlled manner, adjusting valve position as necessary and noting the position of the radiopaque capsule marker band and paddle attachment
  - Warning: Use the blue actuator to deploy and recapture the bioprosthesis. Do not use the trigger for deploying or recapturing because it could cause inaccurate placement of the bioprosthesis
  - Note: Slight repositioning of a partially deployed bioprosthesis (before the radiopaque capsule marker band reaches the distal end of the paddle attachment) can be achieved by carefully withdrawing the catheter
  - Caution: Use the catheter handle to reposition the bioprosthesis. Do not use the outer catheter shaft
  - Before the radiopaque capsule marker band reaches the distal end of the paddle attachment, evaluate the bioprosthesis position
  - Note: During deployment, the blue actuator clicks as a notification before the radiopaque capsule marker band reaches the paddle attachment
  - Either complete bioprosthesis deployment or initiate bioprosthesis recapture
  
- **Medtronic CoreValve™ Evolut R™ Recapture (Optional)**
  - The bioprosthesis should only be recaptured and redeployed a maximum of 2 times. The bioprosthesis can be recaptured a third time to remove the bioprosthesis from the subject
  - Rotate the blue actuator in the opposite direction of the arrows to recapture the bioprosthesis
  - Warning: Use the blue actuator to deploy and recapture the bioprosthesis.
  - Do not use the trigger for deploying or recapturing because it could cause inaccurate placement of the bioprosthesis
  - Continue rotating the blue actuator until the gap between the capsule and catheter tip is closed
  - Caution: Stop advancing the capsule once the gap to the catheter tip is closed. Advancing the capsule farther could damage the capsule
  - Reposition the recaptured bioprosthesis at the optimal depth relative to the valve annulus
  - Deploy the bioprosthesis
  - Either complete bioprosthesis deployment or initiate bioprosthesis recapture. If the bioprosthesis has been recaptured 2 times and then deployed in a non-optimal position, recapture and withdraw the bioprosthesis

- *Medtronic CoreValve™ Evolut R™ Post Deployment*
  - Close the catheter capsule before withdrawal
  - Caution: Close the capsule until it is aligned with the catheter tip. Do not overcapture the catheter tip, because it could interfere with catheter withdrawal through the introducer
  - Withdraw the catheter until the capsule meets the distal end of the EnVeo InLine™ sheath
  - Withdraw the catheter and EnVeo InLine™ sheath together, and dispose of the device in accordance with local regulations and hospital procedures
  - Perform routine aortogram to assess the bioprosthesis for proper expansion and function per the Aortogram Acquisition Guidelines located in **Appendix R.6**

Ballooning as needed during the implant procedure is standard practice and should not be considered a reintervention.

### **Immediate Post-Procedure**

The procedure is considered complete after final angiography has been performed, and the introducer/InLine sheath has been removed from the subject. Thereafter, if an introducer/InLine sheath is re-introduced, this is considered a repeat intervention, which must be documented on the reintervention Electronic Case Report Form (eCRF).

- Coronary Arteriogram
- Following the current recommendation all patients with prosthetic heart valves need endocarditis prophylaxis
- All patients should receive Deep Vein Thrombosis (DVT) prophylaxis with Heparin/Low Weight Molecular Heparin (LMWH) starting approximately 6 hours after TAVI if bleeding permits
- Anticoagulants should be discontinued per hospital standard
- Activated clotting time (ACT) should be monitored per hospital standards but recommendation is >250 seconds
- Cardiac Enzymes: CK within 8-12 hours post procedure and at any time when a clinical ischemic event is suspected.
  - CK-MB is required if CK is elevated  $\geq 2X$  the laboratory upper limit of normal.
  - If a clinical event is confirmed, a total of 3 draws of cardiac enzymes within the first 24 hours (drawn approximately every 8 hours) following the clinical event should be obtained
- 12-lead Electrocardiogram (ECG) to be performed within 48 hours of procedure
- Abbreviated Neurological Assessment
  - National Institute of Health Stroke Scale (NIHSS) to be completed with 24 hours of procedure
- Transthoracic Echocardiogram (TTE)
  - Comprehensive transthoracic 2D echocardiogram (TTE) should be performed within 24-48 hours post-procedure or prior to discharge to assess device success. Echocardiograms will be performed according to Echocardiography Procedures found in **Appendix R.7**
- It is recommended that subjects are treated for a minimum of three months with dual anti-platelet medication
  - If the patient is on warfarin therapy post-procedure it is recommended that subjects are prescribed either daily:
    - Aspirin (75 to 325 mg) **or**
    - Clopidogrel (75 mg) (or ticlopidine, if clopidogrel is contraindicated) for at least three months following the procedure
  - If the patient will **not** be on warfarin therapy post-procedure it is recommended that subjects are prescribed daily:
    - Aspirin (75to 325 mg) **and**
    - Clopidogrel (75 mg) (or ticlopidine, if clopidogrel is contraindicated) for at least three months following the procedure
- Concomitant medications
- Adverse events review
  - Document all adverse events, including all unanticipated adverse device effects (UADE) or unanticipated serious adverse device effects (USADE), technical observations, reinterventions or repeat admissions to the catheterization suite and deaths
  - Any patient with evidence of a new neurological event should have a neurology consult and subsequently an imaging trial if deemed necessary by the neurologist or stroke specialist
  - Any patient exposed to substantial radiation dose levels, as outlined in **Appendix R.23**, should be assessed for skin reactions

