**EnVeo R Catheter Delivery System with EnVeo Inline Sheath**

The EnVeo R delivery catheter system facilitates the placement of the TAV within the annulus of the aortic valve. The catheter assembly is flexible and compatible with a 0.035 in (0.889 mm) guidewire. The distal (deployment) end of the system features an atraumatic, radiopaque catheter tip and a capsule that covers and maintains the bioprosthesis in a crimped position. The capsule includes a distal flare to enable full recapture of the bioprosthesis after partial deployment. A stability layer is fixed at the handle and extends down the outside of the catheter shaft. It provides a barrier between the retractable catheter and the introducer sheath and vessel walls, thus enabling the catheter to retract freely.

The EnVeo R Inline Sheath is assembled over the stability layer, which functions as a hemostatic introducer sheath and minimizes the access site size to the capsule diameter. The EnVeo R Inline Sheath is also compatible with an 18 Fr introducer.

The delivery catheter system consists of a catheter with an integrated handle to provide the user with accurate and controlled deployment. The handle is on the proximal end of the catheter and is used to load, deploy, recapture, and reposition the bioprosthesis. The handle features a gray front grip used to stabilize the system. The blue actuator turns to deploy the bioprosthesis precisely. Arrows on the actuator indicate the direction of rotation required to deploy the bioprosthesis. If desired, the blue actuator can be turned in the opposite direction to recapture the bioprosthesis if the radiopaque capsule marker band has not yet reached the distal end of the spindle. The blue actuator also features a trigger, which can be engaged to make macro adjustments to the capsule position. A blue hand rest connects to the blue actuator. The end of the handle features a tip-retrieval mechanism, which can be used to withdraw the catheter tip to meet the capsule after the device has been fully deployed.

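### The TAVI post-procedure list recommends an ACT above 250 seconds after sheath removal, most likely an in-procedure target placed in the wrong list

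*Combined protocol and SAP*

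**What the plan says.** Section C.4.7.1 of the protocol deals with anticoagulation during and after TAVI in two places.

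- **TAVI Procedure, Vascular Access.** Anticoagulant is given according to the hospital's protocol. If heparin is used, ACT is checked at five minutes and then every 30 to 60 minutes after the first bolus. ACT is to be kept at 250 seconds or more.
- **Immediate Post-Procedure.** The list begins by defining completion: "The procedure is considered complete after final angiography has been performed, and the introducer/InLine sheath has been removed from the subject". Putting a sheath back in after that counts as a repeat intervention. Further down the list comes "Anticoagulants should be discontinued per hospital standard", and directly after it "Activated clotting time (ACT) should be monitored per hospital standards but recommendation is >250 seconds". The bullet before these two starts heparin or low-molecular-weight heparin for DVT prophylaxis about 6 hours after TAVI, if bleeding allows.

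For CoreValve, access closure comes before this list, at the end of the post-deployment steps: "Remove the 18Fr introducer sheath and complete the puncture site closure per hospital protocol". For Evolut R, the delivery catheter and InLine sheath are withdrawn together, also before the list.

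**The concern.** A list that starts with the sheath already out should not carry an ACT target meant for catheter work. Here it does, right after a bullet that has anticoagulants stopped. A site following the number literally would aim for the level used during implantation in a patient whose large-bore access has just been closed. What is at stake is the clarity of an operative safety instruction. Major or life-threatening bleeding is among the endpoints tested for labeling claims (item 15 in section C.6.10.1), so the instruction touches an area the trial measures. That is context only; the documents give no basis for claiming an effect on that comparison.

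**Working it through.** No arithmetic applies: the plan states no bleeding rate, no relation between ACT and bleeding, and no number of sites that would act on the line. The check is a comparison of the text.

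1. **When the list starts.** Its opening sentence requires both final angiography and removal of the introducer or InLine sheath. On a plain reading the bullets apply after that.
2. **The two neighbouring bullets.** One has anticoagulants discontinued. The next recommends an ACT above 250 seconds and gives no time limit. Stopping the drug and aiming for that level pull in opposite directions.
3. **The DVT bullet.** Prophylactic heparin begins only about 6 hours later and only if bleeding allows. That sequence presumes procedural anticoagulation has ended.
4. **Where the number also appears.** The vascular access steps use the same 250-second threshold, as a level to maintain. The post-procedure bullet repeats it in substance.
5. **Whether other procedural items have strayed into the list.** Its first bullet is a coronary arteriogram, which the schedule of assessments (Table 3) places in the procedure column for TAVI subjects. This supports misplacement as the explanation.
6. **The surgical arm.** The SAVR post-procedure and medication lists in section C.4.7.2 contain no ACT target, and the surgical considerations leave the ACT on bypass to the institution. Nothing there suggests that a post-procedure ACT level was intended in this trial.
7. **What follows sheath removal.** For CoreValve, contrast angiography of the access vessels through the reference pigtail comes after the 18Fr sheath is out, and the pigtail and 6Fr introducer are removed after that. For Evolut R, a routine aortogram follows withdrawal of the InLine sheath. This bears on how far a correction should go.

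Steps 1 to 6 support removing the number from the post-procedure list. Step 7 argues against adding a new cut-off elsewhere.

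**The case against.** The best defence is that the conflict is practical and not strict. Both bullets defer to hospital standards, the figure is only a recommendation, and no bullet tells anyone to keep giving procedural heparin. The completion sentence also serves to classify re-entry as a reintervention, so it need not time-stamp every bullet; the coronary arteriogram shows that the list mixes in procedural items. Implant teams must have completed at least 30 TAVI procedures (section C.3.4) and are unlikely to be misled. All of this stands, and it keeps the point minor. It does not justify leaving the number there: the bullet defers to the hospital on monitoring and then sets a figure against that deference.

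A reader might infer more in three directions, none of which the documents support.

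- **That the in-procedure target needs an explicit end at primary-sheath removal.** The only timing limit beside that target concerns the start: "Anticoagulant may be administered at any time prior to this point, but avoid delaying beyond this point". But the target sits under the TAVI Procedure heading, and the completion sentence and the discontinuation bullet bound it. A cut-off at sheath removal would be a new clinical rule, earlier than the protocol's own definition of completion, with angiography still to come.
- **That the target omits Evolut R.** The access step names one device ("The primary access artery will be used to introduce the CoreValve device and the balloon catheter"), and the Evolut R steps begin afresh with "Prepare the vascular access site according to standard practice". Yet the heading is general, and section E.1.2 adds "The EnVeo R Inline Sheath is also compatible with an 18 Fr introducer". Any gap is a matter of missing detail.
- **That the two signs, at least 250 and more than 250, set different standards.** The difference is trivial and disappears when the duplicate is removed.

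**Conclusion.** The point holds as a minor wording error in an operative instruction. The ACT recommendation is most likely an in-procedure item placed in the post-procedure list; taken literally, it points to procedural-level anticoagulation after access closure. Its size cannot be quantified from the documents, and the practical hazard is limited for the reasons above. A reader might infer that the protocol orders heparin to continue after closure, or that TAVI bleeding results would be distorted; the text contains no such order and offers nothing from which to estimate such an effect. The primary analysis, sample size and type I error are unaffected. The conclusion rests on a plain reading of the list as starting at completion. The Instructions for Use (Appendix R.22) are not reproduced in the text reviewed and could say more about ACT management.

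**What to change.** In C.4.7.1, Immediate Post-Procedure, delete the clause of the ACT bullet that begins with the word but and gives the figure of more than 250 seconds. Keep the rest of that bullet, so that ACT monitoring follows hospital standards, and keep the discontinuation bullet unchanged. Leave the 250-second target only in the vascular access steps, with no added end point tied to removal of the primary sheath. The cost is one phrase in the next amendment: no new data, visits or patients. The benefit falls to implants still to be done, and the documents do not say how many remain.
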